#### Purpose:

We propose to perform a study to validate the accuracy and clinical usefulness of the EUM device by comparing it with simultaneous use of current methods (both external or internal devices) among obese patients and patients with normal body mass indexes (BMI). Our goal is to show that the EUM device is a noninvasive tool of similar utility to the fetal scalp electrode and the IUPC, and superior the traditionally used noninvasive devices (Doppler ultrasound and tocodynamometer).

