## Materials and Methods:

This will be a prospective observational study of women presenting for care to Montefiore Medical Center. Patient enrollment will occur during their obstetric triage encounter or on admission to labor and delivery. Patients will be approached if they meet the enrollment criteria. Once informed consent is obtained and the standard methods of fetal and labor assessment are in place the electrodes of the EUM will be attached to the abdominal skin surface. The electrodes will remain in place until delivery or discharge from the hospital if the patient is found not to be in labor and is discharged undelivered.

Patients will be monitored simultaneously with the EUM device and currently used methods (external or internal devices) as clinically indicated by the standard of care. Providers will be blinded to the results of the EUM device and will continue care as per current guidelines using the information obtained from the current monitoring methods. Data from the EUM devices will be captured on a study laptop computer as will data generated by the currently used fetal/uterine monitor to allow for comparison of the two systems. Each patient will serve as her own control for comparison as the data obtained from the two monitoring systems simultaneously will be compared. Patients will be monitored for 30 minutes once they consent in the labor and delivery triage rooms or labor and delivery rooms. Patients will also be asked to complete a device experience and satisfaction survey comparing the methods of monitoring. Assuming the number of minutes of unreadable tracing for the EUM is less than the Doppler by 1 minute, the standard deviation of difference in minutes by the two devices is 3 minutes, and there are 2 obstetrician readings per subject, to reach a power of 80% with 0.05 significance level, 39 patients will be needed for our primary outcome as listed below. It is anticipated that within 6-12 months, this number can be reached with recruiting efforts at both Weiler and North campus. To maximize recruitment, the co-investigator will be present daily on L&D and triage to recruit patients.

Maternal demographics to be obtained will include maternal age, ethnicity, BMI, gestational age, current medications, mode of delivery, birth weight, Apgar scores,

Version 5.13; June 19, 2020

newborn outcome, medical history and any antenatal complications, past surgical history, and postpartum course.

Primary Outcomes:

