- Continuity in readings of fetal heart rate (as measured in the number of minutes without a readable tracing in a 30 minute sample tracing) between EUM and fetal scalp electrode and external fetal heart rate monitoring from the same patient
- Continuity in readings of contractions (as measured in the number of minutes without a readable tracing in a 30 minute sample tracing) between EUM, IUPC and external tocodynamometer from the same patient

Secondary Outcomes:

- Compare average frequency of contractions between the monitoring systems
- Compare duration of contraction between the monitoring systems
- Compare maximum height of the contraction between the monitoring systems
- Compare total Montevideo units obtained between the monitoring systems
- Compare the timing of the contraction between the monitoring systems
- Compare average fetal heart rate between the monitoring systems
- Compare baseline heart rate between the monitoring systems
- Compare the number accelerations between the monitoring systems
- Compare the number of decelerations between the monitoring systems
- Compare the timing of the accelerations between the monitoring systems
- Compare the timing of decelerations between the monitoring systems
- Compare the maximum fetal heart rate achieved during acceleration between the monitoring systems
- Compare the lowest fetal heart rate achieved during deceleration between the monitoring systems
- Compare the degree of variability in the tracing between the monitoring systems. Degree of variability will be defined as the correlation between the tracings. The tracings will be broken down into 4 minute intervals and defined as minimal, moderate or marked variability and compared with each other for accuracy and

Version 5.13; June 19, 2020

consistency. Most accurate will be the internal monitor in each case, i.e. fetal scalp electrode.

- Compare patient satisfaction between the monitoring systems

Inclusion criteria:

- 1) Maternal age >18 years old
- 2) Singleton pregnancy
- 3) Gestational age of 24 completed weeks or greater based on the estimated due date as calculated from last menstrual period or early ultrasound
- 4) Category I (reassuring) fetal heart rate tracing at time of enrollment

Exclusion criteria:

- 1) Fetal anomaly or chromosome defect
- 2) Allergy to silver
- 3) Woman with implanted electronic device of any kind
- 4) Irritated skin or open wound on the abdominal wall

Recruitment Mechanisms:

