#### Device Description:

The EUM300 is composed of three units: Disposable electrode, Maternal unit and Interface unit.

Disposable electrode applied part – Proprietary bio-compatible patch electrode array with nine Ag/AgCl and hydrogel connections. Electrode is made by US based manufacturers: Lead-Lok, Sandpoint, ID and Molex, Naperville, IL.

Maternal Unit – The maternal unit is connected via a proprietary connector to the electrode. The EMG signals are amplified by an analog front-end. OB-Tools Algorithm runs on a DSP board and the result – Fetal Heart Rate and Uterine Activity are transmitted via Bluetooth. The unit contains a 4.2V Li-Ion rechargeable battery. The battery allows 24h of work and must be charged away from the patient.

Interface unit – Wall mount unit translates the information received from a paired Bluetooth Maternal unit. In this setup the EUM is used as a secondary system, one that

Version 5.13; June 19, 2020

is not involved with clinical decisions. In this case a PC computer receives the bluetooth transmission from the maternal unit and saves it into an Excel readable file. A primary monitor that is used for clinical decisions may also be connected to the PC and its data is recorded into the same file for comparison. The file format is a simple 6 column format: Date, Time, EUM UA, EUM FHR, Monitor UA, Monitor FHR. The file can be read and analyzed using Excel, Matlab and other statistical tools.

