**Statistics:**

Routine parametric and non parametric statistical analysis will be performed. Given that each patient serves as her own control (since we will be comparing the EUM device to the routinely used devices simultaneously), we will be able to limit the number of women enrolled.

To assess the improvement in continuity of readings in EUM, continuity in readings will be compared between EUM, Doppler, and FSE from the same patients. Assuming the number of minutes of unreadable tracing for the EUM is less than the Doppler by one minute, the standard deviation of difference in minutes by the two devices is three minutes, and there are two obstetrician readings per subject, to reach a power of 80% with 0.05 significance level, 39 patients will be needed for our primary outcome as listed below.

Regarding assessment of contractions, continuity in readings will be compared between EUM and IUPC in the same patients. To assess the improvement in continuity of readings in EUM, continuity in readings (yes or no) will be compared between EUM and

Version 5.13; June 19, 2020

IUPC from the same patients. A McNemar test will be used to compare the proportion of continuity between these two methods. With N=55 patients, the study will have at least 80% to detect an odds ratio of 3.2 associated with continuity between EUM and IUPC with a two-sided type I error rate of not more than 5%, assuming 50% of discordant pairs. It is acknowledged that the study has only adequate power to detect a substantial difference between EUM and Doppler, and between EUM and IUPC however, anything below this level would be of less clinical interest and the result we obtain from this study will be used to design more definitive studies in the future. Thus, the number of patients required to address each of the aims of the study is as below:

1. Fetal heart rate monitoring: EUM device v. external monitor v. FSE n = 39
2. Contraction monitoring: EUM device v. external monitor n = 55 obese and n = 55 nonobese subjects; EUM device v. intrauterine pressure catheter n = 55 obese and n = 55 nonobese subjects.
3. Productive v. non-productive contractions: EUM device v. external monitor n = 55 subjects.

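### The fetal heart rate primary outcome depends on obstetricians' readings of what is readable, and the plan does not say that the readers are masked to device

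*Combined protocol and SAP*

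**What the plan says.** In Materials and Methods, under Primary Outcomes, continuity of the fetal heart rate reading is defined "as measured in the number of minutes without a readable tracing in a 30 minute sample tracing". Continuity of the contraction reading is defined in the same terms. Neither definition names a reader or says what makes a minute readable.

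The reader appears only in the sample-size text for EUM against Doppler, in Materials and Methods and again in Statistics, which assumes that "there are two obstetrician readings per subject". The fetal heart rate outcome therefore rests on human reading.

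The only masking statement is in Materials and Methods: "Providers will be blinded to the results of the EUM device and will continue care as per current guidelines". It covers clinical care.

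Device Description specifies the recording: "The file format is a simple 6 column format: Date, Time, EUM UA, EUM FHR, Monitor UA, Monitor FHR". The section on the setup with a dedicated notebook adds that the program may show the four signals in real time. The de-identification under Data management concerns patient information, not which device made the tracing.

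The Purpose section gives the hoped-for result: "Our goal is to show that the EUM device is a noninvasive tool of similar utility" to the internal devices, and superior to the usual external ones.

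**The concern.** Whether a minute of tracing is readable is a judgement, and the plan gives no criterion for it. The plan does not prevent a reader from seeing which tracing is EUM, seeing it beside its comparator, and knowing which result is hoped for. Using each woman as her own control removes differences between women. It does not remove a difference in how strictly the two devices' tracings are read, because that difference is part of each paired difference. Averaging two readers reduces random reading error but not a tendency that both share.

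Adding patients does not help either: the shift stays fixed while the standard error shrinks. At stake is whether a significant result on this outcome reflects the device or the reading.

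**Working it through.** **Inputs from the plan (Statistics).** Planned difference of 1 minute; SD of the paired difference 3 minutes; two readings per subject; power 80%; significance level 0.05; 39 patients; paired t-test for continuous outcomes.

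**Assumptions, not in the plan.** Two-sided test (sidedness is not stated for this calculation). The SD of 3 applies to one reader's device difference. The correlation ρ between the two readers' differences lies between 0 and 1. The reading shift b is constant; its size and direction are unknown.

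**Step 1: reproduce the 39.** The variance of the mean of two readings is 9(1 + ρ)/2. The normal formula is n = SD²(1.960 + 0.842)²/1² = SD² × 7.849.

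- ρ = 0: SD² = 4.5, so n = 35.3, rounded up to 36. The paired t-test needs 38.
- ρ = 0.10: SD² = 4.95, so n = 38.9, rounded up to 39. The paired t-test needs 41.
- ρ = 1 (the second reading adds nothing): SD² = 9, so n = 70.6, rounded up to 71. The paired t-test needs 73.

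The stated 39 is therefore reproduced, within 2 patients, if the two readings are averaged and nearly uncorrelated.

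**Step 2: add a shift when there is no true difference.** The standard error is SD/√39, the noncentrality is b divided by the standard error, and the critical value is t(0.975, 38 df) = 2.024. The rejection probability comes from the noncentral t distribution, both tails.

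| ρ | SD of mean | Standard error | Noncentrality at b = 0.25 / 0.5 / 1 | Error rate at b = 0.25 | b = 0.5 | b = 1 |
|---|---|---|---|---|---|---|
| 0 | 2.121 | 0.340 | 0.74 / 1.47 / 2.94 | 11.1% | 30.0% | 81.8% |
| 0.5 | 2.598 | 0.416 | 0.60 / 1.20 / 2.40 | 9.0% | 21.6% | 64.9% |
| 1 | 3.000 | 0.480 | 0.52 / 1.04 / 2.08 | 8.0% | 17.4% | 52.8% |

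With b = 0 the rate is 5.0% in every row. A shift of 0.5 minute is half the planned effect and 0.5/30 = 1.7% of the tracing. The row closest to the plan's own sample size is ρ = 0, where the inflation is largest.

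**Step 3: the other direction.** If the true difference is 1 minute in favour of EUM and the readers are 0.5 minute stricter with EUM, the net difference is 0.5 minute. Power at 39 patients is then the b = 0.5 column: 30% instead of 82% at ρ = 0, and 17% instead of 53% at ρ = 1.

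**The case against.** The strongest reply is that the documents are silent, and silence is not evidence of unmasked reading. That is correct. A reader might infer that the obstetricians will know which tracing is EUM. No section says so, and the size and direction of any bias cannot be learned from the plan. What stands is a missing safeguard on a judged primary outcome.

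Three other stronger readings are tempting and not supported:

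- **That both primary outcomes are read by two obstetricians.** This is stated only for EUM against Doppler. For contractions no reader is named, and the concern applies only if those tracings are also read by eye.
- **That the error rates above carry over to the contraction aim.** Statistics powers that aim with a McNemar test on continuity as yes or no, with 55 patients, and gives no SD in minutes. The calculation does not apply there.
- **That blinding the bedside providers is beside the point.** The Introduction says that external monitors depend on keeping their placement on the abdomen. Staff who reposition a sensor change its unreadable minutes, so blinding them to EUM results does protect this outcome. It does not cover the people who later read the tracings.

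It can also be said that the study is observational, that it is meant to inform more definitive studies, and that both signals are stored digitally, so masked or automated re-reading stays possible after data collection. This limits the severity. It does not close the gap, because the plan commits to neither.

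**Conclusion.** The concern holds for the fetal heart rate primary outcome as an unspecified safeguard: the plan relies on obstetrician readings, blinds only care providers and does not mask the readers to device. At 39 patients with an SD of 3 minutes and no true difference, a shift of 0.5 minute would raise the two-sided error rate from 5% to 17–30%, and a shift of 0.25 minute to 8–11%. The ranges run from fully correlated to uncorrelated readings. These figures illustrate sensitivity and do not estimate a bias that is known to exist. For contractions the point is conditional on visual reading. The change should be made: it is cheap, and it protects the outcome on which the device comparison rests.

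**What to change.** 1. Plot the EUM and monitor signals from the common CSV file in one neutral format, with the same scales, device labels removed and a random code on each tracing.
2. Have the same two obstetricians read each tracing separately, in random order, masked to device and to the paired tracing.
3. Prespecify one criterion for a readable minute, applied to all devices. Say how disagreement is handled and report agreement between the two readers.
4. As a reader-free sensitivity analysis, report missing-signal minutes computed directly from the CSV file.
5. State who or what determines readability for the contraction outcome. If it is read by eye, apply the same procedure.

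The cost is a short plotting script and a randomised reading list, with no extra readers and no change to the sample size. The limitation is that masking may be incomplete if a device's trace looks distinctive, which is why the fourth item is needed.

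### The contraction primary outcome is defined as unreadable minutes for three devices, but the N = 55 behind it comes from a yes/no McNemar test with no cut-off, for EUM v IUPC only

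*Combined protocol and SAP*

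**What the plan says.** The Primary Outcomes list under Materials and Methods gives the endpoint as "Continuity in readings of contractions (as measured in the number of minutes without a readable tracing in a 30 minute sample tracing"), compared between EUM, IUPC and external tocodynamometer in the same woman.

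The Statistics section then narrows the comparison: "Regarding assessment of contractions, continuity in readings will be compared between EUM and IUPC in the same patients". It also changes the scale: "continuity in readings (yes or no) will be compared between EUM and" IUPC, using a McNemar test. The power statement is that with 55 patients "the study will have at least 80% to detect an odds ratio of 3.2 associated with continuity between EUM and IUPC", two-sided 5%, with half of the pairs discordant.

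The list of sample sizes is introduced by "Thus, the number of patients required to address each of the aims of the study is as below". It includes "Contraction monitoring: EUM device v. external monitor n = 55 obese and n = 55 nonobese subjects", and the same 55 + 55 for EUM v IUPC.

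Later in the same section, the amount of discontinuous tracing appears among further comparisons made alongside continuity. A general sentence assigns the paired t-test to continuous outcomes.

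The fetal heart rate primary outcome is worded in the same way as the contraction one, but it is sized in minutes: a 1-minute difference, "the standard deviation of difference in minutes by the two devices is three minutes", and "there are 2 obstetrician readings per subject".

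**The concern.** The calculation that justifies 55 does not concern the variable the protocol calls primary. Three things follow.

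- **No cut-off.** A tracing with two unreadable minutes could count as continuous or not. Yes may mean no gap at all, but the plan does not say so. The dividing line can therefore be set after the data are seen.
- **Two scales, no ranking.** The yes/no result and the minutes result can disagree, and the plan does not say which decides the primary outcome.
- **One comparator sized.** The Purpose section aims to show EUM superior to the tocodynamometer, and the endpoint names that device. The only contraction power calculation is for the IUPC. The 55 + 55 for the external monitor appears to be carried over, with no effect size or power of its own. The Objectives restrict only Montevideo units to EUM v IUPC, so that restriction does not explain the omission. This is the smaller point.

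**Working it through.** **1. The plan's own figure.** Inputs from the Statistics section: odds ratio 3.2, discordant share pd = 0.50, two-sided alpha 0.05, power 80%.

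- Discordant split: 0.50 × 3.2/4.2 = 0.381 and 0.50 × 1/4.2 = 0.119, so d = 0.262.
- N = [1.96·√pd + 0.842·√(pd − d²)]² / d² = [1.386 + 0.553]² / 0.0686 = 54.8, rounded up to 55.
- Asymptotic power at 55 is 80%. An exact McNemar test would have 75%.

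The figure reproduces, so the arithmetic is not at fault.

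**2. Why the missing cut-off matters.** At a fixed odds ratio of 3.2, the result depends heavily on the discordant share:

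| Discordant share | N for 80% power | Power at 55 |
|---|---|---|
| 20% | 141 | 41% |
| 30% | 93 | 57% |
| 40% | 70 | 70% |
| 50% | 55 | 80% |

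A cut-off moves the discordant share and the odds ratio together. The documents give no distribution of unreadable minutes, so the following is an illustration on an assumed one: exponential gaps with means of 2 v 3 minutes, Gaussian copula correlation 0.3, rounded to whole minutes and capped at 30.

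| Counted as continuous if unreadable minutes are | Discordant share | Odds ratio |
|---|---|---|
| 0 | 26% | 1.7 |
| ≤1 | 41% | 2.0 |
| ≤2 | 39% | 2.2 |
| ≤3 | 32% | 2.5 |
| ≤5 | 18% | 3.3 |

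Other assumptions give other values. The table shows only that both inputs depend on the cut-off. It does not show that 50% is unattainable, or that a yes/no test generally loses power.

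**3. What 55 delivers on the defined scale.** The documents give no SD for contraction minutes, so a range is shown. SD 3 is borrowed from the fetal heart rate calculation. The test is a two-sided 5% paired t-test with n = 55, one reading per woman, and noncentrality Δ·√55/SD.

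| SD of difference (min) | Detectable at 80% (min) | Power for 1 min | 95% CI half-width (min) |
|---|---|---|---|
| 2 | 0.77 | 95% | 0.54 |
| 3 | 1.15 | 68% | 0.81 |
| 4 | 1.54 | 44% | 1.08 |

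For example, the half-width at SD 3 is 2.005 × 3/√55 = 0.81.

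**4. If two readings are averaged.** The plan states two readings for fetal heart rate only. If SD 3 applies to a single reading and the readers correlate at ρ, the effective SD is 3·√((1 + ρ)/2).

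| ρ | Effective SD | Detectable at 80% (min) | Power for 1 min |
|---|---|---|---|
| 0 | 2.12 | 0.82 | 93% |
| 0.5 | 2.60 | 1.00 | 80% |
| 1 | 3.00 | 1.15 | 68% |

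**The case against.** The strongest reply is that the minutes analysis is already planned. The Statistics section says the amount of discontinuous tracing will be compared, assigns the paired t-test to continuous outcomes and allows non-parametric methods in general. It never labels McNemar the primary test. The tocodynamometer comparison is also planned, in the Objectives, the endpoint definition and the sample-size list. All of this is correct, and it narrows the fault: a method for the defined scale exists. But that method is generic, has no difference, SD or power attached for contractions, and is listed beside secondary variables. Nothing says that it decides the primary outcome.

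The plan also concedes that it can detect only a substantial difference and will inform later studies. That excuses modest power, but not an undefined primary variable.

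Two further points stand in part. First, keeping the yes/no variable with a prespecified cut-off, and rewriting the endpoint to match, would also remove the mismatch. Minutes is preferred because it is the protocol's own definition and matches the fetal heart rate primary. Second, keeping 55 has a price: for 1 minute at SD 3 with one reading, 80% power needs 73 women per group. Staying at 55 means accepting a detectable difference of 1.15 minutes, or averaging two readings.

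**Conclusion.** The concern holds and should be corrected. The N = 55 calculation is right for the test it describes, but that test is not of the defined primary endpoint, has no cut-off, and covers one of two comparators. Those conclusions rest on the text alone. The size in minutes is conditional: about 1.15 minutes detectable per BMI group at SD 3 with one reading, 0.77 to 1.54 minutes over SD 2 to 4, and 0.82 to 1.15 minutes with two averaged readings at SD 3. The SD is borrowed from another signal and another comparator.

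**What to change.** In the Statistics section:

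- Name the paired difference in unreadable minutes per woman, with 95% CI, as the primary contraction analysis. Use a paired t-test, with the Wilcoxon signed-rank test as a check for skew.
- Report it separately for EUM v tocodynamometer (superiority) and EUM v IUPC, within each BMI group.
- Keep McNemar as supportive, with its cut-off in minutes fixed before any data are seen.
- Keep 55 per group and restate what it delivers in minutes, naming the SD and the number of readings per woman.
- For EUM v IUPC, where the Purpose section aims to show the two are alike in usefulness, present the CI (half-width about 0.81 minutes at SD 3 with one reading). A non-significant difference should not be read as similarity.

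**Cost.** Wording only: no new data, no added enrolment, and the ceiling of 220 patients is unaffected. There are two downsides. The SD is borrowed, and if many tracings have no gap, the minutes test can have less power than a zero-gap yes/no test. The four comparisons are those the plan already lists. If the team chose to split alpha across them (0.05/4 = 0.0125 each), the detectable difference at SD 3 with one reading would rise from 1.15 to 1.39 minutes.

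### The aim of showing EUM similar to the scalp electrode and IUPC has only difference tests for continuity, with no margin, interval or rule for a non-significant result

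*Combined protocol and SAP*

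**What the plan says.** The Purpose section sets a two-part goal. The first part is similarity to the invasive devices: "Our goal is to show that the EUM device is a noninvasive tool of similar utility to the fetal scalp electrode and the IUPC". The second is superiority to Doppler and tocodynamometer.

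Under Primary Outcomes (in Materials and Methods), continuity is the primary outcome against both invasive devices, for fetal heart rate and for contractions. For contractions it reads "Continuity in readings of contractions (as measured in the number of minutes without a readable tracing in a 30 minute sample tracing"; the fetal heart rate outcome uses the same measure.

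The Statistics section then gives:

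- **EUM v IUPC.** The aim is improvement and the outcome becomes binary: "To assess the improvement in continuity of readings in EUM, continuity in readings (yes or no) will be compared between EUM and" (the second device named is the catheter). The test is "A McNemar test will be used to compare the proportion of continuity between these two methods". With 55 patients, "the study will have at least 80% to detect an odds ratio of 3.2 associated with continuity between EUM and IUPC", two-sided at 5% with half of the pairs discordant. The size is 55 obese and 55 nonobese.
- **EUM v FSE.** No test is named for this pair. The general sentence assigning a paired t-test to continuous outcomes applies. The comparison shares n = 39, which was derived from a 1-minute gain over Doppler and an SD of 3 minutes.
- **Limits.** The plan concedes limited power: "It is acknowledged that the study has only adequate power to detect a substantial difference between EUM and Doppler, and between EUM and IUPC". Of smaller effects it says: "anything below this level would be of less clinical interest and the result we obtain from this study will be used to design more definitive" (the sentence goes on to refer to later research).

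The nearest thing to an agreement analysis is the secondary outcome on heart rate variability: "Degree of variability will be defined as the correlation between the tracings", with a comparison of variability categories. It does not concern continuity.

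**The concern.** A difference test starts from no difference and can only reject it. That suits the superiority half of the goal, which is not in question. It does not suit the similarity half, because failing to reject may mean that the devices perform alike or that the study could not tell.

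A significant result favouring EUM would support continuity at least as good as the internal device. If the devices perform alike, which is what the Purpose section sets out to show, the expected result is non-significant. The plan does not say it will read such a result as similarity, but it gives no other rule. The risk is that a noninvasive device is reported as matching the reference devices when the data are also compatible with materially worse continuity.

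**Working it through.** **1. The plan's own figures reproduce as difference tests.**

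McNemar inputs (Statistics): discordance ψ = 0.50, odds ratio 3.2, two-sided 5%, power 80%.

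- Difference in proportions: d = ψ(OR − 1)/(OR + 1) = 0.5 × 2.2/4.2 = 0.262, or about 26 points.
- n = [1.960 √ψ + 0.842 √(ψ − d²)]²/d² = [1.960 × 0.707 + 0.842 × 0.657]²/0.262² = 54.8, so 55, with power 80.2%.

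For n = 39 (1 minute, SD 3, two readings treated as independent, so SD 3/√2), a paired t-test needs 38, against the 39 stated. Neither calculation contains a margin.

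**2. How often McNemar is non-significant.** Unconditional binomial enumeration, ψ = 0.50, two-sided 5%. Each cell runs from the asymptotic to the exact test. The 110 column assumes that the BMI groups are pooled.

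| EUM truly worse by | 55 pairs | 110 pairs |
|---|---|---|
| 0 points | 95-97% | 95-96% |
| 10 points | 81-87% | 68-73% |
| 15 points | 64-72% | 39-44% |
| 20 points | 42-52% | 14-17% |
| 26 points (size of the plan's effect; the test is two-sided, so direction does not matter) | 18-25% | about 2% |

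Which of these deficits is material is an assumption; the documents do not say.

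The result is sensitive to discordance. At an assumed 20%, a 10-point deficit is non-significant in 63-73% (55 pairs) and 32-41% (110 pairs), and a 15-point deficit in 25-35% (55 pairs).

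**3. What an interval would show.** With no true difference, the 95% half-width is 1.96 √(ψ/n): 1.96 √(0.5/55) = 0.187 and 1.96 √(0.5/110) = 0.132, or about 19 and 13 points.

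**4. The same question in minutes.** Paired t-test, true EUM deficit of 1 minute, noncentral t. The SD of the mean of two readings is SD × √((1 + ρ)/2). Ranges run from ρ = 0 (independent readings) to ρ = 1 (fully correlated). SD 3 is borrowed from Doppler; SD 4 and 5 are assumed. Two readings per contraction tracing are also assumed.

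| n | Quantity | SD 3 | SD 4 | SD 5 |
|---|---|---|---|---|
| 39 (FSE) | Non-significant | 18-47% | 42-67% | 59-77% |
| 39 (FSE) | 95% half-width, min | 0.7-1.0 | 0.9-1.3 | 1.1-1.6 |
| 55 | Non-significant | 7-32% | 27-56% | 46-69% |
| 55 | 95% half-width, min | 0.6-0.8 | 0.8-1.1 | 1.0-1.4 |
| 110 | Non-significant | 0.2-7% | 4-26% | 16-45% |
| 110 | 95% half-width, min | 0.4-0.6 | 0.5-0.8 | 0.7-0.9 |

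Example at n = 39, SD 3, ρ = 1: half-width = 2.024 × 3/√39 = 0.97 minutes, almost the whole 1-minute effect planned for Doppler.

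**The case against.** The strongest reply is that similar utility is a broad phrase used once, in Purpose. Objectives and Secondary Outcomes speak only of comparing, and Statistics frames the continuity comparison as improvement, for which a two-sided McNemar test is coherent. On that reading a null result is not the expected one. This shows that Purpose and Statistics disagree about what is to be shown against IUPC. It does not supply an analysis for the goal as Purpose states it.

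Second, the plan admits limited power, plans more definitive studies, and calls smaller differences less interesting. That lowers the urgency, and the last remark could be read as an informal indifference zone. But it is not set as a margin, tied to an interval or turned into a decision rule. If it were a margin, EUM could be about 26 points worse and still count as similar, which the sponsor would have to justify.

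Third, a paired t-test is usually reported with a mean difference and interval, and the plan also allows routine nonparametric methods. An interval may therefore appear in practice, but no rule for interpreting it is planned.

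Fourth, the McNemar figures depend on the 50% discordance. This stands: at 20% they fall as shown above, though the direction is unchanged. The 95-97% under equality is essentially one minus alpha and is not peculiar to this plan; the fault is that no reading of that outcome is planned.

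**Conclusion.** The concern holds and should be fixed. The sample sizes are adequate reproductions of difference tests; the fault is that a stated aim of similarity has no analysis able to support it when the devices perform alike. At 55 pairs and the plan's discordance, a non-significant McNemar result is nearly as likely with EUM 10 points worse (81-87%) as with no difference (95-97%). It becomes uncommon only near the plan's 26-point effect. For FSE at n = 39, a true 1-minute deficit would be missed in 18-47% of studies at the borrowed SD of 3, and more often if the SD is larger.

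The size rests on assumptions the documents do not settle: what deficit is material, the discordance actually seen, the SDs for IUPC and FSE, the correlation between readings, and pooling across BMI groups. The conclusion that non-significance cannot show similarity rests on none of them.

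**What to change.** In Statistics, for EUM v IUPC and EUM v FSE:

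- Make the paired difference in unreadable minutes, with its 95% confidence interval, the similarity analysis. This is the primary outcome already defined.
- State that a non-significant McNemar or t-test will not be read as similarity.
- Conclude non-inferior continuity only if a margin is justified and fixed before analysis and the upper limit for EUM minus the internal device lies below it.
- If no margin can be justified, reword the similarity goal in Purpose as estimation with confidence intervals, without a claim to have shown similarity.
- Limit any such conclusion to continuity, not accuracy.
- Keep the difference tests against Doppler and tocodynamometer.

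The cost is wording in two sections, using data already collected; the interval and the interpretation rule need no extra patients. Whether a margin could be met depends on a margin and SDs that the documents do not give. As illustration only, with an assumed 1-minute margin, true difference 0 and one-sided 0.025, power at n = 39 from fully correlated to independent readings is 53-82% at SD 3, 33-58% at SD 4 and 23-41% at SD 5. The downside is that similarity becomes harder to claim, and for FSE at n = 39 it may be possible to report only the precision achieved.
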